## 7.5 30-day Follow-up (Clinic Visit)

All subjects will return to the clinic at 30 days ( $\pm 7$  days) post-procedure for a clinical evaluation. The 30-day follow up visit will include the following assessments:

- Anginal status (CCS, Braunwald classification of unstable angina, or silent ischemia)
- Current concomitant medication documentation. If DAPT has been interrupted or terminated the stop date (and resumption date, if applicable) and the reason for interruption/termination should be recorded.
- A 12-lead electrocardiogram (ECG)

- Laboratory testing per site standard practice; if laboratory testing is part of the standard of care and includes CBC and serum creatinine, these should be recorded. The results of any additional tests performed per site standard practice should also be collected.
- Documentation of any adverse events/ serious adverse events occurring since the previous evaluation. All clinically significant adverse events should be carefully documented by the research staff using the adverse event data forms. In the event of repeat intervention after the index procedure or repeat diagnostic cardiac catheterization (regardless of whether revascularization was performed), procedural angiographic images should be forwarded to the Angiographic Core Laboratory. For all adverse events that represent a potential endpoint event, all relevant medical information (including clinically relevant imaging data, ECG data, and the results of relevant laboratory testing performed as part of the standard of care) should be collected and retained as part of the research file to support adverse event analysis and adjudication.

Prior to concluding the visit, research staff should also review the follow-up requirements with the subject to help ensure that the patient can be reached for the required telephone contact at 6 months, and that the patient returns to the clinic for the 12-month follow-up visit.

## **7.6 Six-month Follow-up (Telephone Contact/Clinic Visit)**

All subjects will be contacted by telephone at 6 months ( $\pm$  30 days) post-procedure for additional follow-up, to include the following assessments:

- Anginal status (CCS, Braunwald classification of unstable angina, or silent ischemia)
- Current concomitant medication documentation. If DAPT has been interrupted or terminated the stop date (and resumption date, if applicable) and the reason for interruption/termination should be recorded.
- Documentation of any adverse events/ serious adverse events occurring since the previous evaluation. All clinically significant adverse events should be carefully documented by the research staff using the adverse event data forms. In the event of repeat intervention after the index procedure or repeat diagnostic cardiac catheterization (regardless of whether revascularization was performed), procedural angiographic images should be forwarded to the Angiographic Core Laboratory. For all adverse events that represent a potential endpoint event, all relevant medical information (including clinically relevant imaging data, ECG data, and the results of relevant laboratory testing performed as part of the standard of care) should be collected and retained as part of the research file to support adverse event analysis and adjudication.

If a clinic visit occurs as part of the subject's regular medical care during the specified follow-up window, the follow-up assessment may be conducted during this visit, and no separate telephone contact is necessary.

## **7.7 Twelve-month Follow-up (Clinic Visit or Optional Telephone Contact / Virtual Visit\*)**

All subjects will return to the clinic at 12 months ( $\pm$  30 days) post-procedure for a clinical evaluation with the following exceptions:

- For the duration of the Coronavirus Disease 2019 (COVID-19) pandemic, phone follow-up or virtual visit at 12 months is permitted if necessary to assure the safety of trial participants. The reason for the conduct of the phone follow-up should be documented in the eCRF.

The 12-month follow up visit will include the following assessments:

- Anginal status (CCS, Braunwald classification of unstable angina, or silent ischemia).
  - For subjects undergoing this assessment via phone or virtual visit, anginal status should be documented according to patient reporting.
- Current concomitant medication documentation. If DAPT has been interrupted or terminated the stop date (and resumption date, if applicable) and the reason for interruption/termination should be recorded.
  - For subjects undergoing this assessment via phone or virtual visit, concomitant medications should be documented according to patient reporting.
- A 12-lead electrocardiogram (ECG).
  - For subjects undergoing this assessment via phone or virtual visit, the patient should be asked about any recent or planned visits to a healthcare provider. If yes, contact information should be requested and the provider should be contacted to provide any relevant documentation. All documentation should be reviewed with the site Principal Investigator and, if deemed valid, entered into the EDC by the site.
- Laboratory testing per site standard practice; if laboratory testing is part of the standard of care and includes CBC and serum creatinine, these should be recorded. The results of any additional tests performed per site standard practice should also be collected.
  - For subjects being assessed by phone or virtual visit, this data will not be collected.
- Documentation of any adverse events/ serious adverse events occurring since the previous evaluation. All clinically significant adverse events should be carefully documented by the research staff using the adverse event data forms. In the event of repeat intervention after the index procedure or repeat diagnostic cardiac catheterization (regardless of whether revascularization was performed), procedural angiographic images should be forwarded to the Angiographic Core Laboratory. For all adverse events that represent a potential endpoint event, all relevant medical information (including clinically relevant imaging data, ECG data, and the results of relevant laboratory testing performed as part of the standard of care) should be collected and retained as part of the research file to support adverse event analysis and adjudication.
  - For subjects undergoing this assessment via phone or virtual visit, if potential SAEs or AEs are reported, the subject should be asked about any associated healthcare visits; if applicable visits are reported, contact information should be sought and the provider contacted to provide relevant source documentation (including angiographic films, as applicable). All source documentation must be reviewed with the site PI and, if deemed valid, entered into the EDC by the site. All collected angiographic films are provided to the Angiographic Core Laboratory for analysis.

Prior to concluding the visit, research staff should also review the follow-up requirements with the subject to help ensure that the patient can be reached for the required telephone contact (or optional clinic visit) follow-ups at 2, 3, 4, and 5 years. Telephone numbers, including all home, work, and primary physician numbers, should be confirmed.

Note: For subjects who did not receive any study stent during the index procedure (BuMA DES or DP-EES), the 12-month follow-up will be the final follow-up assessment for this protocol.

## 7.8 Annual Follow-up at 2, 3, 4, and 5 Years (Telephone Contact/Clinic Visit)

All subjects who received any study stent during the index procedure will be contacted by telephone (or optional in-clinic assessment) annually at 2, 3, 4, and 5 years post-procedure for additional follow-up, to include the following assessments:

- Anginal status (CCS, Braunwald classification of unstable angina, or silent ischemia)
- Current concomitant medication documentation. If DAPT has been interrupted or terminated the stop date (and resumption date, if applicable) and the reason for interruption/termination should be recorded.
- Documentation of any adverse events/ serious adverse events occurring since the previous evaluation. All clinically significant adverse events should be carefully documented by the research staff using the adverse event data forms. In the event of repeat intervention after the index procedure or repeat diagnostic cardiac catheterization (regardless of whether revascularization was performed), procedural angiographic images should be forwarded to the Angiographic Core Laboratory. For all adverse events that represent a potential endpoint event, all relevant medical information (including clinically relevant imaging data, ECG data, and the results of relevant laboratory testing performed as part of the standard of care) should be collected and retained as part of the research file to support adverse event analysis and adjudication.

NOTE: For subjects who underwent a phone follow-up at the 12-month time point for any reason, it is preferable that the 2-year follow-up be conducted as an in-clinic visit. For all other subjects, if a clinic visit occurs as part of the subject's regular medical care during the specified follow-up window, the annual follow-up assessment may be conducted during this visit, and no separate telephone contact is necessary.

## 8.0 Adverse Events and Serious Adverse Events

In this study, patients should be encouraged to report adverse events (AEs) spontaneously or in response to general, non-directed questioning. Any time during the study, the patient may volunteer information that resembles an adverse event (AE). If it is determined that a clinically significant AE has occurred, the investigator should obtain all the information required to complete the AE CRFs. Non-clinically-significant adverse events will not be required post discharge from the initial study procedure.

### 8.1 Adverse Events (AE)

An adverse event is any untoward medical occurrence, unintended disease or injury or any untoward clinical signs (including an abnormal laboratory finding) in subjects, users or other persons, whether or not related to the study device.

**NOTE:** This definition includes events related to the study device or to the procedures involved, but does not imply that there is a relationship between the adverse event and the study device.

#### *Pre-Existing Conditions:*

Pre-existing medical conditions or a repeat of symptoms reported prior to the procedure will not be recorded as an AE. Pre-existing conditions that worsen during a study are to be considered adverse events. For users or other persons, this classification is restricted to events related to the study device.

## 8.2 Serious Adverse Events (SAE)

A serious adverse event is an adverse event that:

1. Led to a death
2. Led to a serious deterioration in the health of the subject that:
  - a. Resulted in a life-threatening illness or injury
  - b. Resulted in a permanent impairment of a body structure or a body function
  - c. Required in-patient hospitalization or prolongation of existing hospitalization
  - d. Resulted in medical or surgical intervention to prevent life-threatening illness or injury or permanent impairment to body structure or a body function.
3. Led to fetal distress, fetal death or a congenital abnormality or birth defect.

## 8.3 Adverse Device Effect (ADE)

An adverse device effect is an adverse event related to the use of a medical device. This includes:

- Any adverse event resulting from insufficiencies or inadequacies in the Instructions for Use, the deployment, the implantation, the installation, the operation, or any malfunction of the medical device
- Any event that is a result of a use error or intentional misuse

## 8.4 Serious Adverse Device Effect (SADE)

A serious adverse device effect is an adverse device effect that has resulted in any of the consequences characteristic of a serious adverse event.

## 8.5 Unanticipated Adverse Device Effect (UADE)

An unanticipated adverse device effect is any serious adverse effect on the health or safety or any life-threatening problem or death caused by, or associated with, a device, if that effect, problem, or death was not previously identified in nature, severity or degree of incidence in the investigational plan or application (including a supplementary plan or application), or any other unanticipated serious problem associated with a device that relates to the rights, safety or welfare of subjects.

NOTE: An anticipated serious adverse device effect (ASADE) is a serious adverse device effect which by its nature, incidence, severity, or outcome has been identified in the investigational plan or application (including a supplementary plan or application).

## 8.6 Device Deficiencies, Malfunctions, and Use Error

Investigators are instructed to report all possible device deficiencies, malfunctions, misuse or use error observed during the course of the trial. These incidents will be documented in the case report form provided as follows:

- **Device deficiency:** Inadequacy of a medical device related to its identity, quality, durability, reliability, safety or performance. NOTE: Device deficiencies include malfunction, use error, and inadequate labeling. They may or may not affect device performance or lead to an adverse event.
  - **Device malfunction:** Failure of an investigational medical device to perform in accordance with its intended purpose when used in accordance with the Instructions for Use or protocol. NOTE: A device malfunction occurs when the device is used in

compliance with the Instructions for Use, but does not perform as described in the Instructions for Use.

- **Use error:** Act or omission of an act that results in a different medical device response than intended by the manufacturer or expected by the user. NOTE 1: Use error includes slips, lapses and mistakes. NOTE 2: An unexpected physiological response of the patient does not itself constitute a use error.
  - **Device misuse:** Any use of the investigational device by an investigator that is contradictory to the application described in the Instructions for Use will be categorized as device misuse. This is a form of Use Error.

## 8.7 Documentation

Adverse events must be listed on the appropriate CRF. All AEs will be characterized by the following criteria:

- Intensity or Severity
- Relatedness
- Outcome
- Treatment or Action Taken

### 8.7.1 Intensity or Severity

The following categories of the intensity of an adverse event are to be used:

Mild	Awareness of a sign or symptom that does not interfere with the patient's usual activity or is transient, resolved without treatment and with no sequelae.
Moderate	Interferes with the patient's usual activity and/or requires symptomatic treatment.
Severe	Symptom(s) causing severe discomfort and significant impact of the patient's usual activity and requires treatment.

### 8.7.2 Relatedness

The investigator will use the following definitions to assess the relationship to the study device or procedure:

Not related	The cause of the AE is known and the event is not related to the study device or procedure.
Unlikely to be related	There is little or no temporal relationship to the study device or procedure, and/or a more likely alternative etiology exists.
Possibly related	There is a reasonable possibility that the event may have been caused by the study device or procedure. The AE has a timely relationship to the study device or procedure(s); however, follows no known pattern of response , and an alternative cause seems more likely or there is significant uncertainty about the cause of the event.

Related	A related event has a strong temporal relationship and an alternative cause is unlikely.
----------------	--------------------------------------------------------------------------------------------------------

If the relationship between any adverse event and the use of the investigational medical device is considered to be possibly related or related, that event will be classified as an ADE or SADE.

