## 4.0 Background

### 4.1 Clinical Background

Percutaneous coronary intervention (PCI) with drug eluting stents (DES) is a mainstay of treatment for patients with coronary artery disease (CAD), including stable angina, silent ischemia, and acute coronary syndromes (ACS). Compared with bare metal stents (BMS), DES reduce restenosis and the consequent need for repeat revascularization via the inhibition of neointimal hyperplasia. However, even with the use of DES repeat intervention is required in >10% of all patients within 1 year, and DES use has been associated with a small incremental risk of late (>30 days to 1 year post-implantation) and very late (>1 year post-implantation) stent thrombosis. Although rare, stent thrombosis is a devastating complication, usually associated with myocardial infarction or death. Extended duration dual antiplatelet therapy (DAPT) is required after DES implantation, with an attendant risk of bleeding complications; however, the risk of stent thrombosis persists following DAPT discontinuation.

DES are also associated with delayed vascular healing, as evidenced by histologic data from autopsy studies of stent thrombosis that reveal persistent fibrin deposition and poor re-endothelialization. While the mechanisms by which DES cause a prolongation of arterial healing are incompletely understood, the permanent presence of a non-erodable polymer drug release matrix is thought to be a contributor to both late stent thrombosis and late restenosis. The polymer has also been implicated in localized hypersensitivity reactions and adverse late vessel wall remodeling. Although second-generation DES with more biocompatible polymers and reduced strut dimensions have improved the extent of endothelialization, concerns regarding late stent thrombosis and delayed vascular healing remain, and a persistent inflammatory response continues to be observed.

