## 5.6 Safety Summaries and Analyses

### 5.6.1 Adverse Events

For site reported adverse events, number of subjects with at least one adverse event will be summarized for all subjects in the AT population overall and by event severity, relation to procedure, and relation to device. In addition, number of subjects with SAEs and UADEs will be summarized for all subjects in the AT population. Subject data listings of all adverse events and serious adverse events, with their relationship to study device/procedure, AE onset date, outcome, and duration will be presented in the data listings.

Site reported death, myocardial infarction, revascularization, stent thrombosis and bleeding events will be summarized in the ITT population as in-hospital events, at 30-days, 6 months, and 1, 2, 3, 4, and 5 years. Descriptive statistics for in-hospital events will include count, percentage, and sample size. Subjects with missing data will be excluded from the denominator. Differences in event rates between the two treatment arms will be summarized descriptively with the difference in percentages, the asymptotic 95% confidence interval for the difference of two percentages, and a p-value based on a chi-squared test. If 20% or more of the expected cell frequencies are less than 5 then a Fisher's Exact Test will be used to test for differences in proportions.

Survival analysis techniques, as detailed in Section 4.3, will be used to analyze the site reported events at 30 days, 6 months, and 1, 2, 3, 4, and 5 years. Summary statistics will include Kaplan-Meier estimated event rates and number of events. The log-rank test will be used for comparing treatments. Hazard ratios and the associated two-sided confidence intervals (Wald's CI) will be estimated by Cox proportional hazards model, including treatment as a covariate.

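### Protocol 8.7.2 relatedness categories overlap at the ADE/SADE line, leave some events unclassified, and do not define timing for a permanent stent

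*Protocol*

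**What the plan says.** Protocol 8.7.2 gives the investigator four categories. *Not related* requires a known cause that is not the device or procedure. The other three read as follows.

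- *Unlikely*: "There is little or no temporal relationship to the study device or procedure, and/or a more likely alternative etiology exists". Either limb is enough.
- *Possibly related*: opens with "There is a reasonable possibility that the event may have been caused by the study device or procedure". It then asks for timely occurrence and the absence of a recognised response pattern, and adds that "an alternative cause seems more likely or there is significant uncertainty about the cause of the event".
- *Related*: strong timing, "and an alternative cause is unlikely".

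The section closes with the rule that an event "considered to be possibly related or related, that event will be classified as an ADE or SADE". The line between ADE and non-ADE therefore runs between *Unlikely* and *Possibly related*.

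Protocol 8.3 defines an ADE with no time limit. Protocol 4.1 associates DES with "very late (>1 year post-implantation) stent thrombosis", 4.4 makes the reduction of late events an aim, and 8.8.1 collects adverse events through 5 years. SAP 5.6.1 summarises site-reported events "overall and by event severity, relation to procedure, and relation to device".

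**The concern.** A causality scale should give each event one rating. Here a likelier alternative cause is a ground for *Unlikely* and also a permitted feature of *Possibly related*, and the two ratings carry opposite ADE/SADE status. No tie-break is given. *Possibly related* also excludes events that match a recognised pattern, which runs against the usual logic of causality: a known device pattern should strengthen suspicion.

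Timing matters in three of the four definitions and is not defined. For a permanent implant it could mean closeness to the procedure or continuing exposure to the stent. With up to 130 sites, the choice will not be made the same way everywhere.

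At stake are the investigator's ADE/SADE status, the EU 48-hour SADE report in Protocol 8.8.2 (due only where local or national rules require it), and the relatedness columns of the SAP 5.6.1 summary.

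**Working it through.** No rate, power or alpha enters this point, and 8.7.2 states no figure to reproduce. The check applies the wording literally to every combination of three features it uses: timing (little or none, timely, strong), alternative cause (more likely, uncertain, unlikely) and response pattern (known, not known). That is 3 × 3 × 2 = 18 combinations.

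Reading choices: strong timing also counts as timely; the elements of *Possibly related* are all required; its opening condition, a reasonable possibility of causation, is taken as met; *Not related* is set aside because it needs a known cause.

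| Timing | Alternative cause | Known pattern | No known pattern |
|---|---|---|---|
| Little or none | More likely | Unlikely | Unlikely |
| Little or none | Uncertain | Unlikely | Unlikely |
| Little or none | Unlikely | Unlikely | Unlikely |
| Timely | More likely | Unlikely | **Unlikely and Possibly** |
| Timely | Uncertain | **none** | Possibly |
| Timely | Unlikely | **none** | **none** |
| Strong | More likely | Unlikely | **Unlikely and Possibly** |
| Strong | Uncertain | **none** | Possibly |
| Strong | Unlikely | Related | Related |

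**Counts.** Two categories: 2 of 18. No category: 4 of 18. Exactly one: 18 − 2 − 4 = 12. All 6 combinations with little or no timing give *Unlikely* only, even when an alternative cause is unlikely. These are counts of wording combinations, not frequencies of events.

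**Do the reading choices matter?** If timely and strong are merged, there are 2 × 3 × 2 = 12 combinations, with 1 overlap (timely, more likely, no known pattern) and 1 gap (timely, uncertain, known pattern). If strong does not count as timely, the 18 give 1 overlap and 5 gaps. If the opening sentence of *Possibly related* were the whole definition, the gap would close for events with a reasonable possibility of causation, but the overlap would remain and widen. The overlap survives every reading.

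**Timing.** Take a stent thrombosis at month 30. If timing means closeness to implantation, the event has little or none and scores *Unlikely*, although 4.1 names this risk. If timing means continuing exposure, the timing condition is met; but if the event follows a recognised device pattern and its cause is uncertain, it lands in a cell marked none. Neither reading makes the scale work for that event.

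**The case against.** The strongest reply is that this is a drafting flaw with limited reach, and much of it stands.

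- **The text does not rate late events as *Unlikely*.** A reader might infer that it does. But 8.7.2 refers to timing relative to the device or the procedure, and a stent in place is a continuing exposure. Down-rating follows from one reading, not from the words alone.
- **The trial's late risk is not measured with this scale.** TLF from 12 months to 5 years is CEC-adjudicated, and TV-MI and ARC stent thrombosis, including very late thrombosis, have definitions that do not use it. An inference that the late results are wrong or arbitrary is unsupported.
- **UADE review does not hinge on the site rating.** Under 8.8.2 the sponsor evaluates reported SAEs for UADE status, and 8.5 defines a UADE without this scale.
- **There is independent relatedness review.** Protocol 10.2 has the CEC adjudicate device and procedure relationship for potential endpoint events; 11.5.3 extends adjudication to all adverse events; 11.4.7 promises a table by CEC-adjudicated relationship.
- **Deliberate rating by arm is constrained.** Under 11.5.2 staff doing follow-up have no access to randomization eCRFs.

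The CEC safeguard is incomplete, however. Sections 10.2 and 11.5.3 disagree on its scope, and neither says that the CEC's judgement replaces the investigator's ADE/SADE status. The table promised in 11.4.7 appears neither in SAP 5.6.1 nor in the SAP's table list, so for adverse-event summaries the SAP specifies only the site rating. None of the replies resolves the overlap or the gap.

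**Conclusion.** The defect is real and narrow. As written, 8.7.2 gives some events contradictory ADE/SADE status and others no category, and it leaves late events to an undefined notion of timing. The overlap does not depend on how the timing terms are graded. The gap assumes that every element of *Possibly related* is required, which is how the sentence reads. Late down-rating assumes that timing means closeness to implantation, and the documents leave that open.

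The effect is confined to investigator ADE/SADE status, the conditional EU SADE route and the site-reported relatedness summary. Sample size, alpha, power and the primary and powered secondary analyses do not change.

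The number of misclassified events cannot be derived from the documents. A reader might build one from the landmark TLF assumptions, but that would only be a ceiling on subjects with late TLF; it says nothing about how many are device-related or how sites would rate them.

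**What to change.** 1. In 8.7.2, remove from *Possibly related* the condition that the event match no recognised response pattern.
2. Apply the categories in order, so that each event gets exactly one:
   - *Not related*: another cause is established.
   - *Related*: a device or procedure cause is probable and alternatives are unlikely.
   - *Possibly related*: neither of the above, and a device or procedure cause is reasonably possible, even if an alternative seems likelier.
   - *Unlikely*: everything else.
3. State that temporal relationship to the device includes continuing exposure to the implanted stent, and that time since implantation alone does not lower the rating.
4. Reconcile the CEC's scope between 10.2 and 11.5.3, and add to the SAP the AE/SAE table by CEC-adjudicated relationship that 11.4.7 promises.

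The order and the residual category make the scale exclusive and exhaustive. Keeping the likelier-alternative clause within *Possibly related* is deliberate: deleting it would move events that can now be ADEs out of that status.

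The cost is a protocol wording change, matching CRF help text and one SAP table. The downside is that somewhat more events will be classed and reported as ADEs or SADEs.
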